### 6.5.2. Rescue Medication

Rescue medication is not allowed on the day prior to Visit 3 (Randomization Visit), on the day of Visit 3, and the day following Visit 3.

In the United States and Canada, protocol-permitted rescue medication will be a choice of senna (oral) or bisacodyl (oral or rectal) that will be dispensed according to the SOA (Section 1.3).

Outside of the United States and Canada, protocol-permitted rescue medication will be a choice of senna (oral), bisacodyl (oral or rectal) or sodium picosulphate (oral) that will be dispensed according to the SOA (Section 1.3). Participants outside of the United States and Canada will have a choice of at least one of these medications. When there is more than one option available, the participants will choose rescue medication(s) at the Preintervention Visit (Visit 2) and study site staff will register the rescue medication in IWRS, where applicable. The study site must contact the IWRS (if applicable) at all subsequent study visits to obtain the protocol-permitted rescue medication to be dispensed to the participant at each visit as needed.

Rescue medication may be taken when at least 72 hours have passed since the participant's previous BM or when their symptoms become intolerable.

Where available, the participant may continue using their original selection received from the study site throughout the duration of the study or may switch to another protocol-permitted rescue medication in coordination with the site staff.

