- Ensure participants have refrained from using rescue medicine on the prior calendar day and on the day of the Randomization (Visit 3) until the time of the clinic visit.
- Remind participants not to use rescue medicine for the remainder of the day and on the next calendar day after the Randomization Visit
- Run the eDiary Eligibility Report to confirm that the participant can be randomized.
- Review use of protocol-permitted rescue medication dispensed in IWRS where applicable. Participants may choose a different protocol-permitted rescue medication at any visit, where available. Additional protocol-permitted rescue medications may be dispensed as needed at any visit.
- Prior to dosing, the investigator or appropriate site staff member will assess Rome IV criteria for Child/Adolescent IBS and/or FC. Assessment result will be captured in the eCRF. Eligibility for the study is not based on this assessment
- Contact the IWRS to obtain the study intervention (bottle number) to be dispensed to the participant based on randomization
- Administer the first dose of study intervention after completion of all Visit 3 assessments and after confirming the participant has fasted for at least 2 hours. Participants may resume eating 30 minutes after receiving their first dose of study intervention at the study site

- Dispense assigned study intervention for this study after the first dose has been administered. Provide study intervention reconstitution instructions for sprinkles to participants and caregivers for participants who may not be able to swallow capsules (Section 10.8)
- Record the date and time the first dose was administered
- Remind participant and caregiver to bring the bottle(s) of the study intervention and rescue medication to the next visit

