9.3 EDIARY COMPLIANCE

Participants will complete the electronic diary (eDiary) twice daily, once in the morning and once in the evening. Participant's eDiary compliance will be assessed based on the number of days with fully completed morning and evening assessments in a specific period. Morning or evening assessments will be considered fully completed if the participant responded to each question in the corresponding morning or evening eDiary. eDiary compliance will be summarized for the Preintervention Period, double-blind Intervention Period, Postintervention Period, and for each week within each period based on the mITT Population.

Compliance for each participant/interval will be calculated using the following formula:

$$\%Compliance = \frac{100 * \# \text{ of days with fully completed morning AND evening eDiary entries within the interval}}{\# \text{ of expected days within the interval}}$$

On randomization day, the morning diary and/or clinic diary will be included in Preintervention Period and the evening diary will be included in the double-blind Intervention Period. On the day after last dose date, the morning diary will be included in the double-blind Intervention Period and the evening diary will be included in the Postintervention Period.

10.0 **EFFICACY ANALYSES**

The efficacy analyses will be based on the mITT Population.

Baseline values for efficacy endpoints related to daily eDiary responses will be derived from the eDiary in the Preintervention Period, specifically the time period from 14 days before randomization up to the time of randomization.

A SBM is a BM that occurs in the absence of laxative, suppository, or enema use on the calendar day of the BM or the calendar day before the BM. A complete spontaneous bowel movement (CSBM) is an SBM that is associated with a sense of complete evacuation.

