The baseline SBM and CSBM weekly rates, stool consistency, straining, and abdominal symptoms (abdominal pain and bloating) will be derived as discussed in Section 16.3 from 14 days prior to randomization and up to randomization (as appropriate). A participant's baseline stool consistency and straining cannot be assessed if the participant does not have at least 1 SBM during the Preintervention Period. For participants who report no SBMs during a study period, the stool consistency and straining assessments will be considered missing for that study period in the analyses. Participants with missing baseline stool consistency and straining will be excluded from the respective stool consistency and straining analyses that involve change from baseline.

Baseline value for the participant-completed global change and severity items, and observer completed global change and severity items, will be based on the last non-missing assessment on or before the date of first dose of study intervention.

An observed-cases (OC) approach to missing postbaseline data will be applied. Sensitivity analyses to handle missing data are planned for only primary and secondary efficacy endpoints and details are provided in Sections 10.1.2 and 10.2.2 for primary and secondary endpoints respectively.

All statistical tests will be 2-sided at 5% level of significance. All confidence intervals will be 2-sided 95% confidence intervals, unless stated otherwise.

Multiplicity adjustment for the overall Type 1 error rate will be based on primary and secondary endpoints. The overall Type 1 family-wise error rate for testing the primary and secondary efficacy endpoints will be controlled at the 5% level of significance (2-sided) using a sequential testing procedure as stated in Table 10-1.

Table 10-1 Sequential Testing Procedure

Step 1 Primary Endpoint: Change from baseline in 12-week SBM frequency rate (SBMs/week) during Study Intervention Period
	
Compare the linaclotide 72 µg dose versus placebo for the primary efficacy endpoint.
 
 • If superiority is demonstrated over placebo at alpha=0.05 (2-sided), proceed to Step 2. • Otherwise stop.

Step 2 Secondary Endpoint: Change from baseline in 12-week stool consistency during Study Intervention Period
	
Compare the linaclotide 72 µg dose versus placebo for the secondary efficacy endpoint.
 
 • Stop

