Nominal p-values will be provided for the other efficacy endpoints as discussed in Section 10.3.

Depending on the enrollment status for FC participants in this study, an interim analysis (IA) for futility may be considered (details in Section 13.0). A futility check in this IA (when performed) will be performed based on the pre-selected non-binding futility boundary. Following a conservative approach, the final analysis will be performed at a slightly reduced alpha level of 0.049 (2-sided) in case this futility IA is conducted. The optional futility IA at 50% information is not planned to stop the study for efficacy.

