The proportion of participants who have an increase from baseline in the percentage of days using rescue medicine or any other laxatives, suppositories, or enemas in the linaclotide dose group during the 12-week Intervention Period will be compared to the proportion in the placebo group using a CMH test controlling for age group. The number and percentage of responders for each study intervention group, the difference in responder rates between the linaclotide group and the placebo group, the corresponding 95% confidence interval, Mantel-Haenszel -based odds ratio and corresponding 95% confidence interval, and the 2-sided p-value associated with the CMH tests will be presented.

Proportion of Participants Who Report Using Rescue Medicines or Any Other Laxative, Suppositories, or Enema During 12-week Study Intervention Period

The proportion of participants who report using rescue medicines or any other laxative, suppositories, or enemas during the Study Intervention Period in the linaclotide group will be compared with the proportion in the placebo group using a CMH test controlling for age group. The similar analyses as discussed for the proportion of participants with an increase in rescue medicine or any other laxatives, suppositories, or enema use will be provided by study intervention group.

Participant-Completed Global Change Items and Global Severity Items at Each Week During Study Intervention Period

The details of participant-completed global change item scores and global severity item scores are discussed in Section 16.3.10. For each of the participant-completed global change items (pooping problems and tummy problems) and global severity items (pooping problems and tummy problems), study intervention comparison (linaclotide versus placebo) will be performed using a CMH test, controlling for age group at each week after randomization during the Study Intervention Period. Counts and percentages for each category within each individual item will be provided by study intervention group.

Change from baseline in the participant-completed global severity items (pooping problems and tummy problems) at each post baseline week during the Study Intervention Period will also be analyzed using the same ANCOVA model as discussed for primary endpoint in main analysis approach (Section 10.1.1).

Observer-Completed Global Change Item and Global Severity Item at Each Week During Study Intervention Period

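### In the FC rescue-increase endpoint, about 10% of baseline days but about 2% of treatment days are rescue-free by rule, which modestly inflates the share labelled as an increase in both arms.

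*SAP*

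**What the plan says.** The endpoint in FC SAP 10.3 is a yes/no label for each participant: "The proportion of participants who have an increase from baseline in the percentage of days using rescue medicine" or any other laxative, suppository or enema. The linaclotide proportion "will be compared to the proportion in the placebo group using a CMH test controlling for age group". A difference in rates, an odds ratio, their confidence intervals and a p-value are also reported. No minimum rise is set, and nothing says which days form the denominator. In the same section, the fecal incontinence endpoint does have its denominator spelled out.

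Baseline for daily eDiary endpoints (FC SAP 10.0) is "specifically the time period from 14 days before randomization up to the time of randomization". FC SAP Table 16-2 starts the Intervention Period after randomization on Day 1, with that evening's diary, and ends it with the morning diary on the day after the last dose.

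Protocol 6.5.2 describes rescue use as "not allowed on the day prior to Visit 3 (Randomization Visit), on the day of Visit 3, and the day following Visit 3". The part before randomization is enforced by exclusion criterion 2.02 (Protocol 5.2) and by a site check at Visit 3 (Protocol 10.10.3). The part after randomization is backed only by a reminder to participants.

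On the endpoint's standing, FC SAP 10.0 says: "Nominal p-values will be provided for the other efficacy endpoints as discussed in Section 10.3".

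**The concern.** The same short ban falls on two windows of very different length. It removes a visible share of a two-week baseline and almost nothing of a twelve-week treatment period. Because any rise counts, a small systematic gap between the two percentages is enough to tip some participants into the increase category when their behaviour has not changed.

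At stake is how the reported percentages read. This is one of two FC endpoints on rescue use. A reader of the study report would take the proportion with an increase as a measure of worsening in each arm, and part of it would come from the calendar.

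**Working it through.** The plan states no figure for this endpoint, so there is none to reproduce.

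**Day counts.** The half-day rule in FC SAP 16.3.4 is written for stool frequency rates. Applying it here is an inference.

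- Baseline: Day -14 to Day -1 plus half of Day 1 = 14.5 days. Barred: Day -1 plus that half day = 1.5. Share barred: 1.5/14.5 = 10.3%.
- Treatment, completer with 84 days of dosing: 0.5 + 83 + 0.5 = 84 days. Barred: the other half of Day 1 plus Day 2 = 1.5. Share barred: 1.5/84 = 1.8%.

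**Expected percentage.** If rescue is used on a fraction r of permitted days throughout, the expected percentage is r × (1 − 1.5/14.5) = 0.897r at baseline and r × (1 − 1.5/84) = 0.982r on treatment. The ratio is 0.982/0.897 = 1.095. One day a week (r = 1/7), for example, moves from 12.8% to 14.0%.

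Other conventions for completers:

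- Day 1 and Day 85 dropped: (82/83)/(13/14) = 1.064.
- Half days counted whole: (83/85)/(13/15) = 1.127.

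For early discontinuers the effect shrinks: (1 − 1.5/28)/(1 − 1.5/14.5) = 1.056 at 4 weeks, and (1 − 1.5/14)/(1 − 1.5/14.5) = 0.996 at 2 weeks.

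**Chance of being labelled an increase with no real change.** The documents give no rescue rate, so daily rates p are assumed, with independent days. Whole days are needed, so 13 permitted baseline days and 82 permitted treatment days are used, with k_b ~ Bin(13, p) and k_i ~ Bin(82, p). As written, the label requires k_i/84 > k_b/14.5. On permitted days it requires k_i/82 > k_b/13.

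| Assumed daily rate | As written | Permitted days only | Difference |
|---|---|---|---|
| 0.05 | 0.585 | 0.546 | 0.039 |
| 0.10 | 0.591 | 0.535 | 0.056 |
| 0.20 | 0.575 | 0.533 | 0.042 |
| 0.30 | 0.584 | 0.510 | 0.074 |

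Outside this range the difference is near zero at 0.02 (0.624 against 0.623) and about 10 points at 3/7 (0.611 against 0.509).

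**A small true fall.** If use on permitted days falls by 8%, the chance of the increase label at the same four rates is 0.564, 0.557, 0.521 and 0.508 as written. On permitted days it is 0.532, 0.497, 0.479 and 0.445.

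**Between-arm difference.** The same model was run for the four rates with six assumed pairs of treatment-period use relative to baseline (placebo/linaclotide 1/0.7, 1/0.5, 0.8/0.5, 0.7/0.4, 0.6/0.4, 0.5/0.3). In 23 of the 24 cases the difference in proportions is as large or larger as written. At rate 0.30 with 1/0.7 it is 0.277 as written against 0.240 on permitted days. The exception is rate 0.10 with 1/0.7: 0.145 against 0.152.

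**The case against.** Four points weigh against making much of this.

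- **Most of the inflation has another source.** Even on permitted days, 51-55% of unchanged users are labelled an increase, because a short, noisy baseline is compared with a long period and no threshold is set. This stands. The ban supplies only the increment, though that increment runs in one direction for completers and can be removed.
- **The ban is the same in both randomized arms.** This stands. A reader might infer that it biases the CMH comparison or blurs the contrast between linaclotide and placebo. The documents give no basis for bias under the null, and the 24 scenarios show that the difference in proportions is generally not reduced.
- **The day counts and the use model are assumptions.** This stands in part. Every day convention tried gives a rise for completers, but the size depends on the pattern of use. Rescue is allowed after 72 hours without a bowel movement or for intolerable symptoms (Protocol 6.5.2), so use is unlikely to be independent from day to day, and use barred on one day may move to a nearby day. For fixed habits of every third, fourth or fifth day, the share labelled an increase is the same under both definitions. For every seventh day it is 5 of 7 starting phases against 1 of 7. An every-second-day habit looks dramatic (all phases against half), but with no ban and the same 14.5- and 84-day denominators it is also labelled an increase in every phase. That example therefore does not isolate the ban.
- **The stakes are low.** This stands. It is an other efficacy endpoint outside the sequential testing procedure. The companion endpoint, any rescue use during treatment, has no baseline and is unaffected.

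**Conclusion.** The point holds as a modest flaw in a descriptive proportion. For completers with an unchanged habit, the expected percentage of rescue days is about 6-13% higher (relative) on treatment than at baseline. At assumed daily rates of 0.05 to 0.30, about 4-7 percentage points of the share labelled an increase in each arm come from the ban. These sizes rest on the borrowed half-day rule, completion of 84 days, constant rates and independent days.

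A reader might infer that any child with an unchanged habit will be recorded as an increase. The documents do not support that. The statement is true of the expected percentage only: about 4 in 10 unchanged users would not be labelled an increase, and a child who never uses rescue cannot be. Nor does the flaw reach the primary or secondary inference. It is a minor point, worth correcting because the correction is cheap.

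**What to change.** In FC SAP 10.3, before unblinding:

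1. Define the percentage of rescue days in both periods over days on which rescue was permitted, leaving Day -1, Day 1 and Day 2 out of numerator and denominator.
2. List separately any rescue use recorded on Days 1-2 after randomization.
3. Beside the CMH test, report change from baseline in this percentage with the ANCOVA already specified in FC SAP 10.1.1.

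Step 1 removes the calendar shift. Step 3 deals with the larger weakness, the any-rise dichotomy: a simulation with assumed rescue rates and a 20% reduction gave power of about 0.78-0.98 for the ANCOVA against 0.36-0.73 for the dichotomy.

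The cost is a few SAP sentences, one changed derivation and one added model, with no new data and no change to the rescue rules. There is a downside: rescue actually taken on Days 1-2 leaves the percentage, hence the separate listing, and the CMH difference may become slightly smaller. The ANCOVA supplies the more precise comparison.

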10.4 SUBGROUP ANALYSIS FOR EFFICACY ENDPOINTS

Primary and secondary efficacy endpoints will be analyzed in a similar way as discussed for main analysis approach (except age not included as factor in the model for age subgroup analyses) for the following subgroups (within each subgroup category) based on the mITT Population if sample size allows.

- Age group (6-11 years group, 12-17 years group)
- Region (North American, EU, and Other),
- Race (white, non-white),
- Gender (male, female)

Due to the reduction in the number of participants included in analyses of subgroups, p-values will not be reported in the presentations of results obtained in subgroup analyses. Subgroups will be interpreted with caution due to limited sample size within each subgroup category.

11.0 SAFETY ANALYSES

The safety analysis will be performed using the Safety Population. The safety parameters will include adverse events (AEs) and clinical laboratory parameters, vital sign (including postural), electrocardiographic (ECG) parameters, height, and weight. For each safety parameter of the clinical laboratory, vital signs, height, weight, and ECG parameters, the last non-missing safety assessment before the first dose of study intervention will be used as the baseline for all analyses of that safety parameter. Continuous variables will be summarized by number of participants and mean, SD, median, minimum, and maximum values. Categorical variables will be summarized by number and percentage of participants. The safety summaries will be provided by study intervention group.

11.1 ADVERSE EVENTS

Adverse events will be coded by system organ class and preferred term using the *Medical Dictionary for Regulatory Activities*, version 23.0 or newer.

An AE will be considered a treatment-emergent adverse event (TEAE) if

- The AE began on or after the date of the first dose of study intervention; or
- The AE was present before the date of the first dose of study intervention, but increased in severity or became serious on or after the date of the first dose of study intervention

An AE that occurs more than 30 days after the last dose of study intervention will not be counted as a TEAE.

An AE will be considered a treatment-emergent serious adverse event (TESAE) if it is a TEAE that additionally meets any SAE criterion.

The number and percentage of participants reporting TEAEs in each study intervention group will be tabulated by descending percentage in any group, by system organ class and preferred term, and further categorized by severity and causal relationship to the study intervention. If more than 1 AE is coded to the same preferred term for the same participant, the participant will be counted only once for that preferred term using the greatest severity and strictest causality for the summarization by severity and causal relationship. The above summaries of TEAEs, further categorized by severity and causal relationship will also be provided within each age group. If there are 5 or less participants with severe or related TEAEs in any study intervention group, the corresponding age group summaries for TEAEs by severity or causal relationship will not be provided.

The incidence of common ($\geq 5\%$ of participants in any study intervention group) TEAEs will be summarized by system organ class, preferred term, and study intervention group.

Summary tables will be provided for participants with TESAEs, AEs of special interest, and participants with TEAEs leading to premature discontinuation of study intervention.

For the Safety Population, separate listings will be presented for participants who died, participants with SAEs, participants with AEs leading to premature discontinuation, and participants with AEs of special interest. AEs during the Postintervention Period will also be included in the listings. Listing of all AEs will also be presented.

